The proposed study will employ a between subjects prospective design to follow 168 Veterans with CUD and co-occurring insomnia over the course of six months while individuals complete a treatment/placebo group within the context of outpatient addiction treatment at the Menlo Park division of the VA Palo Alto Health Care System. Overall, this design will involve assessments during the following times: baseline (prior to the intervention), over the course of the intervention, upon completion of the treatment/placebo group conducted during week 6 (completion of the sleep [or placebo] intervention), and three follow-up assessments conducted 2-weeks, 4-weeks, and 6-months post-treatment. Veterans will be recruited through the outpatient substance abuse treatment program within the Menlo Park Division of the VA Palo Alto Health Care System and through fliers placed throughout the community. Interested participants will complete a brief phone-based screening with a trained research assistant to assess for initial inclusionary/exclusionary criteria. Eligible individuals will then be scheduled for a baseline assessment once enough individuals have been recruited to comprise three groups for the treatment/placebo group portion. Baseline assessments will consist of structured clinical interviews, questionnaires, and a urine toxicology to assess for the presence/absence of marijuana. Eligible participants will then be randomly assigned to one of three conditions: (1) CBT-I with adjunctive sleep mobile app (CBT-I-MA); (2) CBT-I only (CBT-I); or (3) Placebo-control(PC). The treatment/placebo groups will occur weekly for six consecutive weeks. During this time, substance use (including

Title: The Impact of CBT-I on Cannabis Cessation Outcomes
Approval Period: 03/27/2015 - 03/11/2016

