The Impact of CBT-I on Cannabis Cessation Outcomes

[name], P.I.

NCT02102230

**Research Design and Statistical Plan sections
abstracted from CDA application**

Notice of Intention to Fund: 02/24/2014

2a.3. Research Design and Methods

Design Framework.

The proposed study will employ a between subjects prospective design to follow 168 Veterans with CUD and co-occurring insomnia over the course of six months while individuals complete a treatment/placebo group followed by a cannabis cessation attempt within the context of outpatient addiction treatment at the Menlo Park division of the VA Palo Alto Health Care System. Overall, this design will involve assessments during the following times: baseline (prior to the intervention and quit attempt), *over the course of the intervention*, upon completion of the treatment/placebo group conducted during week 6 (completion of the sleep [or placebo] intervention), and three follow-up assessments conducted 2-weeks, 4-weeks, and 6-months post-cessation. Veterans will be recruited through the outpatient substance abuse treatment program within the Menlo Park Division of the VA Palo Alto Health Care System. Interested participants will complete a brief phone-based screening with a trained research assistant to assess for initial inclusionary/exclusionary criteria. Eligible individuals will then be scheduled for a baseline assessment once enough individuals have been recruited to comprise three groups for the treatment/placebo group portion. Baseline assessments will consist of structured clinical interviews, questionnaires, and a lab-based physiological sleep assessment. Eligible participants will then be randomly assigned to one of three conditions: (1) *CBT-I with adjunctive sleep mobile app (CBT-I-MA)*; (2) *CBT-I only (CBT-I)*; or (3) *Placebo-control (PC)*. The treatment/placebo groups will occur weekly for six consecutive weeks. *During this time, substance use (including cannabis) and sleep will be monitored*. Upon completion of the treatment/placebo group (week 6), individuals will complete self-report questionnaires and a sleep assessment. Individuals will then schedule their cessation attempt for the following day. Two-weeks, 4-weeks, and 6-months post-cessation (follow-up assessments) participants will complete home-based sleep assessments (actigraphy) and the same self-report and interview-based questionnaires that were administered during baseline. Assessments will be completed in person. Baseline and 6-month follow-up interviews and questionnaires will take 3 hours to complete, while 2-week and 4-week post-cessation follow-up appointments will take 1 hour. Home-based sleep assessments will occur overnight for the length of each individual's typical sleep cycle (approximately 8 hours).

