Cannabis Use Frequency and Relapse: Timeline follow-back (TLFB; Sobell & Sobell, 1992) will be used to assess past 3 month cannabis use at baseline and at the 2-week, 4-week, and 6-month follow-ups. The TLFB procedure has demonstrated good reliability and validity in past work across diverse samples (Sobell & Sobell, 1992). Cannabis use information obtained from the TLFB will be used as outcome variables for Aim 1. Research has demonstrated that TLFB is as effective as biochemical measures of substance use (Hjorthøj et al., 2012; Hjorthøj, Fohlmann, et al., 2012).

Measures: Sleep Disturbance.

Sleep Diary: The Consensus Sleep Diary (CSD; Carney et al., 2012) will be used to prospectively monitor self-reported sleep. The sleep diary has been deemed the "gold standard" self-report assessment of sleep (Carney et al., 2012). The CSD is a new standardized sleep diary based on expert consensus and qualitative patient input, developed for use across a range of clinical and research settings. The CSD is the primary self-report sleep assessment being used to monitor responses to CBT-I within the VHA roll-out of this treatment. The CSD will be completed daily throughout the course of this study.

Objective Sleep Assessment: Lab-Based Polysomnography (PSG): Lab-based overnight polysomnography will be conducted through the use of the Nihon Kohden Trackit Sleepwalker system to objectively measure sleep and assess for severity of sleep apnea (AHI) during the baseline assessment. This system is a 16-channel, level 2 ambulatory monitoring system that acquires the following signals: EEG (at F3, F4, Cz, Pz), horizontal electroculogram (EOG), chin electromyogram (EMG), Electrocardiogram (ECG), chest circumference (impedance plethysmography), abdominal circumference, nasal pressure, left and right leg movement (via accelerometry), oxygen saturation (SpO₂), and body position (right lateral, left lateral, prone, and supine). Based on these signals we will obtain data on obstructive sleep apnea, sleep staging, body position, total sleep time, and sleep efficiency. Assessment will take place within the sleep

lab of the NCPTSD.

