Negative Affectivity: The negative affect subscale of the 20-item Positive and Negative Affect Schedule (PANAS; Watson et al., 1988) will be utilized to measure negative affectivity. This instrument has shown good internal consistency as well as discriminant and convergent validity (Watson et al., 1988). The PANAS will be administered at all time points to obtain levels of negative affect.

Other Substance Use: In addition to cannabis, Timeline Follow-Back (TLFB; Sobell & Sobell, 1992) will also be used to assess past 3 month use of caffeine, alcohol, tobacco, and illicit drug use during the baseline assessment, and use during weekly assessments and during the 2-week, 4-week, and 6-month post-cessation follow-ups.

Pharmacotherapy Use: The use of pharmacotherapy will be assessed using the prescription medication index (PMI). This measure assesses *class of medication (SSRI/SNRI, benzo, non-benzo hypnotic, trazodone, prazosin, atypical anti-psychotic), dosage, and use since the previous assessment. It is reasonable to expect that the distribution of these prescriptions will not differ across treatment arms after randomization. For classes that do differ, dummy codes will be generated and used in exploratory analyses to evaluate the moderating role of pharmacotherapy on outcomes.*

Table 1. Overview of assessment to be administered at each time point.

		Time Points of Administration
--	--	-------------------------------

Construct	Assessment	Baseline	Weekly During Group	Post- group	2-weeks post-quit	4- weeks post- quit	6-month post-quit
Descriptive Characteristics of the Sample							
Demographics	Demographics	X					
Psychiatric Diagnoses	SCID-I	X					X
Inclusionary/Exclusionary Criteria							
Insomnia Disorder	SCID-I*	X					X
Suicide	SCID-I	X					
Cannabis Use Disorder	SCID-I*	X					X
Motivation to Quit	CL	X					
Sleep apnea	Berlin/PSG	X					
Outcomes: Sleep							
Insomnia Symptoms	CSD	X	X	X	X	X	X
	ACT	X		X	X	X	X
Outcomes: Cannabis Use							
Cannabis Use Frequency	TLFB	X	X	X	X	X	X
Relapse Status	TLFB				X	X	X
Potential Confounding Factors							
Age	Demographics	X					
Era of Service	Demographics	X					
Psychological Diagnosis	SCID-I*	X					
Anxiety Symptoms	IDAS	X		X	X	X	X
Depression Symptoms	IDAS	X		X	X	X	X
Negative Affect	PANAS	X		X	X	X	X
Other Substance Use	TLFB	X	X	X	X	X	X
Pharmacotherapy	PMI	X	X	X	X	X	X

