Note: * = modified to be consistent with DSM-5 criteria. The post-group assessment corresponds to completion of the treatment/placebo groups.

2a.3.j. Planned Data Analysis.

Generalized Linear Mixed Modeling (GLMM) will be used as the primary data analytic approach for Aims 1 and 2. We believe this approach will provide the most parsimonious test of our hypotheses based on the following considerations. First, we considered only evaluating outcomes at the 6-month follow-up. While this approach would provide information regarding long-term outcomes, it has significant limitations including: (a) increased potential for attrition and missing data, and (b) loss of knowledge regarding outcomes immediately after the quit attempt (i.e., 2-weeks, 4-weeks). For these reasons an analysis focusing solely on the 6-month follow-up would not provide the most reliable and powerful test of the hypotheses. Second, *GLMM allows for modeling slope and change over time. This approach will allow us to model change in substance use and sleep over the course of short-term (2-weeks, 4-weeks) and long-term (6-months) follow-up, while also allowing us to model any unpredicted change in substance use (e.g., cannabis) during the treatment/placebo phase.* Based on these considerations we opted to conduct the primary analysis for Aims 1 and 2 by evaluating change over time through the use of GLMM. This analytic approach is favorable for a number of reasons including its ability to include all available data, not just data from patients who complete assessments. In addition, we will conduct secondary analyses for each hypothesis to evaluate group differences at each time point.

To account for family wise error, alpha will be adjusted in all secondary analyses. *Importantly, over the course of group CBT-I (or placebo group), we will track participants' substance use, including cannabis, and sleep. We will model all outcome data from the start of the intervention. This approach will allow for modeling any unpredicted changes in cannabis use (i.e., increase or decrease in use) during the intervention portion of the study.* Below we provide a detailed overview of how GLMM will be employed for Aims 1 and 2.

Aim 1:

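### Read literally, the 3-month timeline follow-back window leaves about weeks 4 to 13 after quit day with no cannabis assessment, so relapse by 6 months cannot be fully derived

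*SAP*

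**What the plan says.** SAP section 2a.3.i, under cannabis use frequency and relapse, states that TLFB "will be used to assess past 3 month cannabis use at baseline and at the 2-week, 4-week, and 6-month follow-ups". It adds that TLFB supplies the Aim 1 outcome variables. Table 1 also lists weekly and post-group TLFB for cannabis frequency, and gives Relapse Status by TLFB at 2 weeks, 4 weeks and 6 months. Neither document defines relapse.

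The SAP design framework sets "three follow-up assessments conducted 2-weeks, 4-weeks, and 6-months post-cessation". The protocol, section 2(a), keeps the same three visits but counts them from the end of treatment: "three follow-up assessments conducted 2-weeks, 4-weeks, and 6-months post-treatment".

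Section 2a.3.j says that the mixed model allows the team to "model change in substance use and sleep over the course of short-term (2-weeks, 4-weeks) and long-term (6-months) follow-up".

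Two other instruments in section 2a.3.i are worded differently:
- For other substances, TLFB covers "past 3 month use of caffeine, alcohol, tobacco, and illicit drug use during the baseline assessment, and use during weekly assessments" and at the follow-ups. Here the 3 months attaches to baseline.
- The medication index (PMI) records drug class, "dosage, and use since the previous assessment".

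**The concern.** If one 3-month window governs every visit, the interviews do not join up. The 4-week interview ends at week 4 and the 6-month interview begins at about week 13. Nothing else planned for cannabis covers the interval: weekly TLFB stops with the group sessions, and the protocol's urine tests are taken only at assessments. The sleep diary, by contrast, is kept daily throughout.

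Reducing lapse and relapse is the trial's stated purpose (protocol section 1(b)), and Table 1 lists relapse status at 6 months among the cannabis outcomes. A Veteran who uses only in weeks 5 to 12 would have no recorded use after quit day and would look the same as one who never used. For someone who starts in the gap and continues, the relapse is seen but its onset is not. Days that the interview does not ask about may not be recoverable later.

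**Working it through.** The plan gives no coverage figure of its own to reproduce, so this is calendar arithmetic.

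**Inputs.** Visits at 2 weeks, 4 weeks and 6 months, and a look-back of 3 months (SAP 2a.3 and 2a.3.i). Take 6 months as 26 weeks and 3 months as 13.

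**Gap.**
- Start of the 6-month window: 26 − 13 = week 13, or day 91.
- Last day covered by the 4-week visit: day 28.
- Uncovered: 91 − 28 = 63 days = 9 weeks; 63/182 = 34.6%.
- If the 4-week visit is missed, the gap starts at week 2: 13 − 2 = 11 weeks.

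**Sensitivity to the calendar.**

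| Reading | 6-month visit | Window starts | Gap |
|---|---|---|---|
| Calendar months | week 26.1 | week 13.0 | 9.0 weeks (35%) |
| 28-day months | week 24 | week 12 | 8 weeks (33%) |
| Calendar months counted from group start | week 20.1 | week 7.0 | 3.0 weeks |

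The last row is considered because the design framework follows Veterans "over the course of six months while individuals complete a treatment/placebo group followed by a cannabis cessation attempt", and "The treatment/placebo groups will occur weekly for six consecutive weeks". It is the less likely reading: the SAP text and Table 1 both date the visit from quitting, and the protocol dates it from the end of treatment.

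**What can still be derived on the literal reading.**

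| Quantity | Derivable? |
|---|---|
| Point prevalence abstinence at each visit (Hypothesis 1.2) | Yes |
| Use frequency in the window before each visit (Hypothesis 1.1) | Yes |
| Relapse present in weeks 13 to 26 | Yes |
| Any relapse since quit day | Not fully; use confined to weeks 4 to 13 is lost |
| Time to first lapse or relapse | Not if onset is in the gap |
| Continuous abstinence, total days of use to 6 months | Not fully |

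**Share of first events that start in the gap.** This needs a hazard shape, which the documents do not give, so two are assumed. Write F(t) = 1 − exp[−H·(t/26)^k], with H = −ln(1 − F(26)). Protocol section 3(a) gives 6-month rates of 63% (lapse) and 71% (relapse).

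| F(26) | k | F(13) − F(4) | Share of events |
|---|---|---|---|
| .71 | 1 (constant) | .461 − .173 = .288 | 40.6% |
| .63 | 1 (constant) | .392 − .142 = .250 | 39.7% |
| .71 | 0.5 (front-loaded) | .583 − .385 = .199 | 28.0% |
| .63 | 0.5 (front-loaded) | .505 − .323 = .182 | 28.9% |

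A relapse rate above the lapse rate is odd if both share a denominator. If, as an assumption, 71% applies only to those who lapsed, overall relapse is .63 × .71 = .447. The constant-hazard figure then falls from about 29 to about 17 per 100 participants.

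**The case against.** The best defence is that no planned analysis needs the missing weeks. Hypotheses 1.1 and 1.2 use frequency and point prevalence abstinence at three assessments. Neither requires an unbroken record from quit day, and with three follow-up visits the short- and long-term modelling is by visit. No hypothesis tests relapse status or time to relapse. Table 1's separate marks at each visit also fit a status at that visit rather than a cumulative one. All of this stands. A reader might infer that relapse status and the long-term course cannot be derived at all; the documents do not support that.

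The second defence is that the sentence is ambiguous. The wording for other substances ties 3 months to baseline, and the cannabis sentence omits the weekly and post-group interviews that Table 1 shows, so it is not a full specification. The cannabis TLFB form is listed among the protocol attachments but is not reproduced, so its window cannot be checked. This also stands, but it does not remove the need for an edit. On that reading the follow-up window of the instrument behind Aim 1 is not stated at all, while the medication index has a clear one.

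Third, a reader might take the 18 to 29 per 100 participants as relapses that would be missed. They are not. They are first events whose onset falls in the gap under assumed hazards. To be missed, a relapse must start after week 4, end before week 13 and be followed by abstinence to week 26. The documents give no basis for estimating how many do.

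**Conclusion.** The point holds in a limited form. On the literal wording, about 9 weeks (35%) of follow-up after quit day have no cannabis assessment; with 28-day months it is 8 weeks (33%). In consequence, cumulative relapse to 6 months, its timing, continuous abstinence and total days of use cannot be fully derived.

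The size rests on two assumptions: that 3 months applies at follow-up, and that 6 months runs from quit day or the end of treatment. If the first fails, the window is unspecified rather than gapped. If the second fails, the gap is about 3 weeks. The 28% to 41% of first events with onset in the gap depends on the assumed hazards and is not an estimate of missed relapses.

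The planned tests of Hypotheses 1.1 and 1.2 can still be run. This is an inexpensive correction to an outcome measure that should be made, not a failure of the primary analysis.

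**What to change.** In SAP section 2a.3.i:
- Run each follow-up cannabis TLFB back to the last completed assessment, the rule that the medication index already follows. At 6 months that is 26 − 4 = 22 weeks, or 24 if the 4-week visit was missed.
- Define relapse: what pattern of use counts, and that status at each visit means any relapse since quit day. Derive it from the continuous daily record. Because the protocol now dates visits from the end of treatment, name the day on which the record starts.
- The look-backs will be about 2, 2 and 22 weeks, so express frequency as a rate per day, or keep the last 3 months as a separate summary comparable with baseline.

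The same edit keeps the 2- and 4-week windows from reaching back before quit day. Under a literal 3-month window only 2 of 13 weeks (15%) and 4 of 13 weeks (31%) are post-quit.

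The cost is a short SAP change, a change to the interview form, and some extra minutes in the existing 3-hour 6-month interview. The real downside is weaker day-level recall for the earliest weeks of a 22-week look-back, which should be acknowledged when relapse dates are reported.

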Hypothesis 1.1. Veterans who receive either *CBT-I-MA* or *CBT-I* prior to a cannabis cessation attempt will evidence a greater reduction in cannabis use frequency over the three post-quit attempt assessments (2-weeks, 4-weeks, and 6-months post-quit day) as compared to those who receive *PC*. In order to test this hypothesis a mixed-effects regression will be used to model changes in the dependent variable (frequency of cannabis use) across time as a function of group membership and baseline values (fixed effects) with a random effect for person to account for repeated measurements; frequency of cannabis use (obtained from TLFB; See 'measures' section for details).

As a secondary analysis, we will conduct an *analysis of covariance (ANCOVA; alpha set to .01)* to examine group differences in cannabis use frequency at each time point (2-weeks, 4-weeks, and 6-months post-cessation).

Hypothesis 1.2. Veterans receiving either *CBT-I-MA* or *CBT-I* will have greater point prevalence abstinence (PPA) over the three post-quit attempt assessments (2-weeks, 4-weeks, and 6-months post-quit day) compared to those receiving *PC*. In order to test this aim we will evaluate the differences in PPA between *CBT-I-MA* and both *CBT-I* and *PC* groups, and *CBT-I* and *PC* groups across the three follow-up assessments (2-weeks, 4-weeks, and 6-months post-cessation). This will be conducted through the use of a mixed-effects logistic regression.

As a secondary analysis, we will conduct three chi-square analyses to examine group differences in rates of PPA at each of the three time points (2-weeks, 4-weeks, 6-months post-cessation).

Exploratory Hypothesis. *In terms of the above cannabis outcomes, those who receive CBT-I-MA will evidence better outcomes (reduced frequency and greater PPA) as compared to those who receive CBT-I. Results related to this hypothesis will be determined through analyses conducted for the primary hypotheses (Hypothesis 1.1 and 1.2).*

Secondarily, we will conduct exploratory analyses to examine factors (e.g., adherence, dose) that account for differences observed between the *CBT-I-MA* and *CBT-I* groups in relation to cannabis outcomes through the use of mediation models. Mediators of interest will include adherence (measured by session attendance), and dose.

Aim 2:

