Hypothesis 2.1. Veterans who receive either *CBT-I-MA* or *CBT-I* prior to a cannabis cessation attempt will evidence improved sleep quality, as indicated by self-report and objective measures, over the three post-quit attempt assessments (2-weeks, 4-weeks, and 6-months post-quit day) as compared to those who receive *PC*. In order to test this hypothesis, two mixed-effects regressions will be conducted, one for self-report sleep (see 'measures' section for details) and another for objective indices of sleep (see 'measures' section for details). First, we will model changes in the dependent variable (self-report or objective sleep) across time as a function of group membership and baseline values (fixed effects) with a random effect for person to account for repeated measurements (random effects).

As a secondary analysis, four ANCOVAs will be conducted to examine differences in self-reported sleep quality between groups at each time point (following 6-week treatment/placebo group, 2-weeks, 4-weeks, 6-months post-cessation attempt). A series of four additional ANCOVAs will then be conducted to examine group-based differences in objective sleep at each time point (following 6-week treatment/placebo group, 2-weeks, 4-weeks, 6-months post-cessation attempt). All ANCOVAs will adjust alpha to account for family wise error rate.

Hypothesis 2.2. *Group based differences in cannabis outcomes averaged across the three post-quit attempt assessments (2-weeks, 4-weeks, and 6-months post-quit day) will be explained*

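### The models for Hypotheses 1.1 and 2.1 take in treatment-phase records but name no term or contrast that isolates the three post-quit visits

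*SAP*

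**What the plan says.** All references are to SAP section 2a.3.j (Planned Data Analysis) unless stated.

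- **Window of the hypotheses.** Under Hypothesis 1.1 the CBT-I arms "will evidence a greater reduction in cannabis use frequency over the three post-quit attempt assessments (2-weeks, 4-weeks, and 6-months post-quit day". Under Hypothesis 2.1 they "will evidence improved sleep quality, as indicated by self-report and objective measures, over the three post-quit attempt assessments".
- **Data in the model.** The introduction to the section says "We will model all outcome data from the start of the intervention". The reason given is: "This approach will allow for modeling any unpredicted changes in cannabis use (i.e., increase or decrease in use) during the intervention portion of the study".
- **Terms in the model.** For Hypothesis 1.1 the outcome is modelled across time "as a function of group membership and baseline values (fixed effects) with a random effect for person". The model sentence for Hypothesis 2.1 has the same structure. Neither names a group-by-time or group-by-visit term, a phase term or a contrast.
- **Time.** The introduction also notes that "GLMM allows for modeling slope and change over time".
- **Records.** "The treatment/placebo groups will occur weekly for six consecutive weeks" (section 2a.3, Design Framework). Table 1 schedules cannabis frequency at baseline, weekly during group, post-group and at three follow-ups. The Measures text on cannabis use (section 2a.3.i) lists the timeline follow-back only at baseline and the three follow-ups. Actigraphy is taken at baseline, post-group and the three follow-ups. The sleep diary is daily.

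**The concern.** The hypotheses and the data entering the model cover different periods, and nothing written in the model links the two. For two primary hypotheses, an analyst could fit one constant group effect, a linear group-by-time slope, or a visit-specific model with a post-quit average. All three are compatible with the text, and they estimate different quantities.

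The constant effect mixes weeks in which SAP participants have not yet been asked to quit with the weeks the hypothesis is about. A real post-quit benefit could be missed, and a significant coefficient could come from treatment weeks alone. Because the choice is open, it could also be made after the data are seen.

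**Working it through.** **1. The plan's own figure.** The Power Analysis says 168 people allow detection of d = .42. The detectable difference at 80% power, two-sided .05, is (1.96 + .842) × √(1/n₁ + 1/n₂):
- 84 v 84: .43
- 56 v 112: .46
- 56 v 56: .53

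Power at d = .42 is .78, .73 and .60 respectively, so .42 is not quite reproduced. It serves below only as a reference effect, and the point does not depend on it.

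**2. Record counts before quit day.**
- Cannabis frequency (Table 1): 6 weekly + 1 post-group + 3 follow-up = 10, of which 7 are before quit day. The Design Framework places the post-group assessment in week 6; if it coincides with the sixth weekly record, the count is 6 of 9. If the Measures text governs, there are no weekly records.
- Actigraphy: 1 of 4.
- Abstinence (Hypothesis 1.2): 0 of 3.
- Diary: daily; how days are grouped for analysis is not stated.

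**3. Constant group effect.** With a random person effect and balanced records, the group coefficient is the plain mean of the visit-specific effects. Let f be the average treatment-phase effect as a fraction of the post-quit effect. The coefficient is then (7f + 3)/10 of the post-quit effect.
- f = 0: 3/10 = 30% (3/9 = 33% with nine records)
- f = .5: 6.5/10 = 65%
- f = 1: 100%
- Actigraphy at f = 0: 3/4 = 75%

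**4. Power.** Assumptions: 56 per arm, standardised outcome, d = .42 at each follow-up, two-sided .05, equal correlation ρ = .5.
- SE of the single coefficient: √[(2/56)(.5 + .5/10)] = .140.
- SE of the three-visit mean: √[(2/56)(.5 + .5/3)] = .154. Then .42/.154 = 2.72, power .78.
- f = 0: .126/.140 = .90, power .15.
- f = .5: .273/.140 = 1.95, power .50.
- f = 1: .42/.140 = 3.00, power .85.

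At ρ = .7 and f = .5, power is .39 against .70. A decaying covariance (person .4, exponential .4 with a 12-week scale, noise .2), fitted by generalised least squares, gives closely spaced weekly records less weight:
- f = 0: .23 (55%), power .34 against .76
- f = .5: .33 (78%), power .58 against .76

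**5. Linear group-by-time slope.** Records are placed at weeks 1–6, 6, 8, 10 and 32 (mean 7.7, sum of squares 722.1). With equal correlation, SE = √[(2/56)(1 − ρ)/722.1], which is .0050 at ρ = .5 and .0039 at ρ = .7.
- Sleep benefit of d = .56 built up evenly to week 6 and then held: slope = .56 × 13.42/722.1 = .0104. Power is .55 (ρ = .5) and .77 (ρ = .7), against .95 and .91 for the three-visit mean. Under the decaying covariance it is .48 against .94.
- Effect of d = .42 only after quit day: slope = .42 × 26.9/722.1 = .0156. Power is .88 and .98, against .78 and .70. The slope test is not weak here, but its coefficient is a rate of change per week, not the post-quit difference.

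**6. Does the fix recover the effect?** In 20 simulated trials of 168 people with ten records, with a true effect of 1 after quit day and 0 before, one group term returned .297. A group-by-phase model on all records returned .991, as did the three follow-ups alone.

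**The case against.** A reader might infer that the SAP fits one constant group effect, that 7 of 10 records precede quit day for every outcome, and that the tested effect is therefore diluted by a known amount. The documents do not support this. A time-constant effect is stated nowhere. The section speaks of slope and change over time, and gives the treatment-phase data their own purpose. With a group-by-phase or group-by-visit term there is no dilution. The 7-of-10 count belongs to cannabis frequency on one reading of Table 1. Every percentage below 100 rests on an assumed in-treatment effect, and for sleep, which CBT-I targets during treatment, a value near 100% is plausible.

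Three further defences have some force.

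- **Large hypothesised effect.** The SAP hypothesises d = 1.4 for Hypothesis 1.1. With 112 v 56 and intraclass correlation .3–.7, power stays at .85–.99 even at the 30% factor. However, the Power Analysis says no research has examined CBT-I's effect on cannabis use, and its 1.4–2.4 range concerns sleep disturbance. Adequate power also does not make the coefficient the right quantity.
- **Post-quit effects appear elsewhere.** Hypothesis 1.2 is confined to the three follow-ups, Hypothesis 2.2 averages over them, and ANCOVAs test each visit. But the ANCOVAs are secondary; for cannabis frequency alpha is .01, where power at d = .42 (56 v 56, unadjusted) is about .36 per visit.
- **Competent analysts would add the contrast.** Perhaps, but a slope is an equally natural reading of the time wording and does not answer the hypothesis.

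What stands is that the models for Hypotheses 1.1 and 2.1 contain no written post-quit estimate.

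**Conclusion.** The concern holds as under-specification of the primary estimate for Hypotheses 1.1 and 2.1, not as proof that a wrong model is planned. The listed terms, taken literally, do not give the post-quit arm difference, and neither does a linear slope from the start of treatment.

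The size is conditional. For cannabis frequency under Table 1 and a single group term, the coefficient ranges from 30% of the post-quit effect (no earlier effect, equal correlation) through about 65–78% (half the effect in treatment) to 100% (full effect throughout). The slope reading costs power mainly when a sleep benefit builds by week 6 and then holds. The effect sizes over time and the correlations are assumptions; the documents give none. For actigraphy the worst case under equal weighting is 75%, and abstinence is untouched.

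Two inconsistencies need reconciling alongside. Table 1 and the Measures text disagree on weekly cannabis follow-back. The SAP counts follow-up from quit day, while the current Protocol (section 2a) counts from end of treatment and its modification summary removes the motivation-to-quit criterion.

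**What to change.** State in section 2a.3.j that the primary estimate for Hypotheses 1.1 and 2.1 is the arm difference averaged over the 2-week, 4-week and 6-month visits. Take it from a mixed model with visit as a category and with group-by-visit and baseline-by-visit terms. Keep weekly and post-group records in their own visit cells, or in a separate treatment-phase model, so that they carry no weight in the primary contrast. This still describes unexpected change during treatment. State the day from which the three visits are counted, in agreement with the current Protocol, and make the Measures text and Table 1 agree on when cannabis use is recorded.

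The cost is SAP wording and a few more model parameters, with no new data. If the effect is in fact constant from the first week, the contrast gives up some power relative to a single coefficient: .78 against .85 in the ρ = .5 example.
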